FFR	Fractional Flow Reserve
GPSP	Good Post-marketing Study Practice
HDL	High Density Lipoprotein
IFU	Instruction for Use
IVUS	Intravascular Ultrasound
LAD	Left Anterior Descending Artery
LCX	Left Circumflex Artery

Acronym/ Abbreviation	Description
LDL	Low Density Lipoprotein
LMCA	Left Main Coronary Artery
LMT	Left Main Trunk
LVEF	Left Ventricular Ejection Fraction
MACE	Major Adverse Cardiac Event
MI	Myocardial Infarction
MLA	Minimal Lumen Area
MLD	Minimum Luminal Diameter
MSCT	Multiple Slice Computer Tomography
MRA	Magnetic Resonance Angiography
NQMI	Non Q-wave Myocardial Infarction
NSTEMI	Non-ST elevation Myocardial Infarction
OCT	Optical Coherence Tomography
PCI	Percutaneous Coronary Intervention
PMS	Post-marketing surveillance
PRU	P2Y12 Reaction Unit
QCA	Quantitative Coronary Angiography
QMI	Q-wave Myocardial Infarction
RCA	Right Coronary Artery
RVD	Reference Vessel Diameter
ST	Scaffold/Stent Thrombosis
STEMI	ST-elevation Myocardial Infarction
SVG	Great Saphenous Vein Graft
TIA	Transient Ischemia Attack
TIMI	Thrombolysis in Myocardial Infarction
TLR	Target Lesion Revascularization
TVF	Target Vessel Failure
TVR	Target Vessel Revascularization

1. PURPOSE

This is a post-marketing use result surveillance (hereinafter referred to as “Surveillance”) conducted per the standards required by the Minister of Health, Labour and Welfare provided in the standards for post-marketing surveillances and studies [except for those defined in the Ministerial Ordinance on Good Clinical Practice for Medical Devices (MHLW Ordinance No. 36, 2005)] based on Paragraph 4, Article 23-2-9 (including application *mutatis mutandis* per Article 23-2-19 of Revised PAL) of the Law on Securing Quality, Efficacy and Safety of Pharmaceuticals and Medical Devices, etc. (Law No. 145, 1960, hereinafter referred to as “Revised PAL”) by the Marketing Authorization Holder or accredited foreign manufacturer of a medical device defined in Paragraph 1, Article 23-2-5 of Revised PAL. The purpose of the Surveillance is to know the frequency and status of adverse device effects and adverse events in order to assure the safety of the new medical device, and to collect efficacy and safety information for evaluating clinical use results.

2. SURVEILLANCE METHOD

2.1 Subjects

Based on the Ministerial Ordinance on Good Post-marketing Study Practice for Medical Device, the Surveillance will **continuously register** patients with ischemic heart disease potentially indicated for treatment with the Absorb GT1 Bioresorbable Vascular Scaffold System ([REDACTED] [REDACTED] hereinafter referred to as “Absorb GT1”).

Only on-label use of the Absorb GT1 will occur in this Surveillance until otherwise allowed by the Sponsor although this is a post-marketing use result surveillance. Detailed patient enrolment eligibility will be determined separately in guidelines.

2.2 Registration Method

[figure not shown]
- The Surveillance may be conducted per site-specific requirements for patient registration to post-marketing surveillance such as provision of information to patients and signed informed consent by patients, if applicable.
- Patient registration will continuously occur when treatment with Absorb GT1 is attempted.
 - Lesions for which treatment with Absorb GT1 was attempted will be target lesions.
 - If an attempt of Absorb GT1 implantation was failed and the treatment was done with other stent/device instead, the background information and procedure information on the Absorb GT1 will be recorded. Follow-up is not required unless any adverse event occurred in relation to the attempted Absorb GT1 implantation.
 - Lesions treated with other stent during the index procedure will be non-target lesions.

- If planning staged implantation (treatment is divided into several times in stages) is performed, the patient registration will occur at the time when treatment with Absorb GT1 is first attempted.
 - If treatment with Absorb GT1 is attempted for initial procedure, it will be the study procedure.
 - If treatment with Absorb GT1 is attempted for additional procedure in addition to the initial procedure, only additional treatment form will be entered.
 - Follow-up is also required for lesions treated with additional procedure. If any adverse events occur, the information will be recorded.
 - If treatment with Absorb GT1 is not attempted for initial procedure but attempted for additional procedure, the additional procedure will be the study procedure. The initial procedure is treated as history.
- De novo lesions observed during follow-up can be treated with Absorb GT1. Such case will not be considered as a new registration.
 - Before starting commercial sale (if ST rate at 3 months is $\leq 0.9\%$, commercial sale will be started), if Absorb GT1 is attempted as the additional procedure during follow-up, only the additional treatment form will be entered.
 - Result of use of Absorb GT1 for treatment of in-scaffold restenosis of Absorb GT1 or stent restenosis of other stent is currently unknown. Do not use Absorb GT1 for restenosis treatment until the Sponsor provides updated information.
 - Follow-up is required for lesions treated with additional procedure. If any adverse events occur, the information will be recorded.
- Quantitative measurement of RVD is strongly recommended for treatment with Absorb GT1
 - If IVUS/OCT is used for RVD measurement, RVD may be measured after pre-dilatation (if difficulty in lesion crossing is predicted)
- Post-procedure IVUS/OCT is strongly recommended until operators became familiar with use of Absorb GT1. **If incomplete scaffold expansion or apposition was observed, consider additional post-dilatation** within the maximum balloon pressure of the device.
- It is not recommended that patients registered in the Surveillance participate in any other therapeutic clinical study. Non-surveillance information/data obtained by the standard procedures of Surveillance Sites (eg, intravascular imaging) can separately be analyzed.
- Scheduled imaging follow-up is not required in the Surveillance. However;
 - When a follow-up imaging is conducted as a scheduled or diagnostic test, the Sponsor may request Surveillance Sites for images and related materials. Surveillance sites will cooperate in providing to the Sponsor, if requested.
 - Absorb GT1 loses strength along with progression of bioresorption. Therefore, after proceeding of bioresorption, intravascular imaging is in principle limited for a diagnostic purpose.

- Absorb GT1 is not visible under X-RAY. Therefore, MSCT or MRA can be used as an initial stenotic diagnosis.

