5.2 Procedural Information

- 1) Basic Procedural Information
- 2) Treated Lesion Information (Per lesion, stenting procedure only. Bifurcation lesion should be regarded as two lesions if both stented)
- 3) Pre-dilatation/Preparation (to be generated per dilatation/preparation)
- 4) Stenting Information (Including attempted but not implanted, to be generated per stent)
- 5) Post-dilatation (to be generated per dilatation)
- 6) Final Results

5.3 Pre- and Post-procedural Cardiac Enzymes**5.4 Procedural Complications****5.5 Antiplatelet Medications after the Procedure****5.6 Other Medications (Pre/Post-procedure)****5.7 Clinical Follow-up****5.8 Imaging Follow-up (target lesion only)**

- 1) Primary imaging modality
- 2) If MSCT/MRA, Restenosis assessment
- 3) CAG
- 4) Intravascular imaging

5.9 Device Malfunction/Deficiency**5.10 Scaffold/Stent Thrombosis****5.11 Adverse Event Other Than ST (to be reported)**

- Coronary Adverse events
 - Ischemia (Angina or ischemic test)
 - Diagnostic Catheter
 - Revascularization
- Bleeding
- Other serious adverse events (including adverse events related to antiplatelet medications)*
- Any adverse events related to Absorb GT1, or their causal relationship is "unknown"

*a serious adverse event: led to death, resulted in a life-threatening illness or injury, requires inpatient hospitalization or prolongation of existing hospitalization for treatment, impairment (e.g. resulted in a permanent impairment of a body structure or a body function) or threatened to impairment, led to a congenital abnormality or birth defect, an important medical event that may not result above but may be considered serious based upon the investigator's appropriate judgment.

For the adverse events described above, the causal relationship with the device or the procedure, adverse events related to antiplatelet medications, and outcomes of every adverse event should be recorded. For serious adverse events, reasons for the judgment of seriousness should be recorded as well.

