5.12 Additional Treatment (If done with Absorb GT1)

If Absorb GT1 is used for treatment in the registered patients before starting commercial use (i.e., before ST rate through 3 months is available for all the registered patients, as primary endpoint), the information should be recorded.

- 1) Type
- 2) Basic Procedural Information
- 3) Treated Lesion Information (Per lesion, stenting procedure only. Bifurcation lesion should be regarded as two lesions if both stented)
- 4) Pre-dilatation/Preparation (to be generated per dilatation/preparation)
- 5) Stenting Information (Including attempted but not implanted, to be generated per stent)
- 6) Post-dilatation (to be generated per dilatation)
- 7) Final Results

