If CK-MB is measured by Site-standards, the definition used in Absorb Japan clinical trial will be used. For other cases, use the Modified WHO definition.

Definition used in the Absorb Japan clinical trial
Classification and criteria of NQMI

Classification	Biomarker Criteria	Additional Criteria
Periprocedural PCI (≤48h post-PCI)	CK-MB >5 x URL	Baseline value* < URL
Periprocedural CABG (≤48h post-CABG)	CK-MB >10 x URL	Baseline value < URL, and any of the following: New pathologic Q waves** or LBBB; new native or graft vessel occlusion; imaging evidence of loss of viable myocardium
Spontaneous All late events that are not associated with a revascularization procedure will be considered simply as spontaneous.	CK-MB > URL, or Troponin*** > URL	One or more of the following must also be present: (a) symptoms of ischemia; (b) development of pathological Q waves** (c) ECG changes indicative of new ischemia - (new ST-T changes or new LBBB), (d) or imaging evidence of a new loss of viable myocardium or a new regional wall motion abnormality
Reinfarction (not related to procedure)	If the CK and CK-MB values are stable or decreasing on 2 samples, a 25% or greater increase 3 to 12 hours after second sample is required to diagnose recurrent MI.	If biomarkers are increasing or peak not reached then insufficient data to diagnose recurrent MI.

URL=Upper Reference Limit
 LBBB=Left Bundle-branch Block
 * Baseline biomarker value is required before study procedure and presumes a typical rise and fall post
 ** If abnormal Q-wave is observed, then adjudicated as Q-MI
 *** If both values are obtained, then CK-MB must be used for adjudication

Modified WHO definition

Elevation of CK > 2 x URL and CK-MB > URL without abnormal Q-wave.

Myocardial infarction - Relation to the Target Vessel

All infarcts that cannot be clearly attributed to a vessel other than the target vessel will be considered related to the target vessel.

Revascularization

The revascularizations in the Surveillance will be adjudicated by Sites per the ARC definition.

- **Location of Revascularization:**

- **Target Lesion Revascularization (TLR)**

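### Routine enzyme and complication data are not specified for further Absorb GT1 procedures, so a silent periprocedural MI after one depends on the site recognising and reporting it

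*Protocol*

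**What the plan says.** Section 2.2 of the protocol deals with two kinds of further Absorb GT1 procedure.

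- **Staged treatment.** The first Absorb GT1 attempt is the study procedure. For a later stage, "If treatment with Absorb GT1 is attempted for additional procedure in addition to the initial procedure, only additional treatment form will be entered". The next item adds: "Follow-up is also required for lesions treated with additional procedure. If any adverse events occur, the information will be recorded".
- **New lesions during follow-up, before commercial sale.** Here "if Absorb GT1 is attempted as the additional procedure during follow-up, only the additional treatment form will be entered". Again, "Follow-up is required for lesions treated with additional procedure. If any adverse events occur, the information will be recorded".

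Section 5.12 sets out what is recorded "If Absorb GT1 is used for treatment in the registered patients before starting commercial use". It lists seven items: type, basic procedural information, treated lesion, pre-dilatation, stenting, post-dilatation and final results.

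Enzymes and complications appear elsewhere in section 5, under headings of their own: "Pre- and Post-procedural Cardiac Enzymes" (5.3) and procedural complications (5.4). Section 5.1 mentions a separate cardiac enzyme form.

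The MI table in Attachment 2 defines a periprocedural PCI infarction as CK-MB > 5 x URL within 48 hours of PCI, with a baseline below URL. Its footnote says: "Baseline biomarker value is required before study procedure".

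**The concern.** A periprocedural MI under the Attachment 2 rule is a laboratory finding. It needs no symptom, ECG change or imaging. Such events are found dependably only if enzyme values before and after the procedure enter the data set as a matter of course. The protocol lists those values among the data to be collected, but its form rule for a further Absorb GT1 procedure, taken at its word, leaves them out.

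Two implants in the same patient could then be held to different standards of MI detection. Section 2.2 makes every lesion with an attempted Absorb GT1 implantation a target lesion, and Attachment 2 assigns an infarction to the target vessel unless it clearly belongs to another. An undetected event could therefore be missing from MI, TV-MI, TLF, MACE, TVF and cardiac death/MI. Any bias would be downward and confined to patients who receive more than one Absorb GT1 procedure. The surveillance exists to establish how often adverse events occur, so uneven detection bears on its purpose.

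**Working it through.** The documents give no figure to reproduce, so the check is mainly a comparison of text.

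**1. Form content.**

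| Data | Study procedure | Further Absorb GT1 procedure |
|---|---|---|
| Procedural details | 5.2, six items | 5.12, the same six items plus type |
| Cardiac enzymes | 5.3 | not listed in 5.12 |
| Procedural complications | 5.4 | not listed in 5.12 |
| Form rule in 2.2 | no restriction | additional treatment form only |

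The absence of enzymes from 5.12 proves little by itself, because 5.2 omits them too. What separates the columns is the last row. No restriction keeps the 5.3 and 5.4 pages from accompanying 5.2. For further procedures, the word *only* in 2.2, taken literally, does keep them out.

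**2. Baseline value.** The periprocedural rule needs a baseline below URL. In a staged case, 2.2 makes the first Absorb GT1 attempt the study procedure. The footnote therefore does not, in words, cover the value before a later implant.

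**3. Routes by which an MI after a further procedure can still be captured.**

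- 2.2 requires adverse events after additional procedures to be recorded.
- 5.11 makes serious events reportable, as well as any event related to the device or of unknown relation. Its coronary items are ischemia, diagnostic catheter and revascularization; MI is not named.
- 7.1 requires entry, in principle within 48 hours, once the site learns of the event.
- 7.5 sends suspected MIs to the clinical events committee for up to 3 years.

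None of these is limited to the study procedure, but each starts with the site noticing or suspecting something. A recognised or symptomatic MI is covered. A silent enzyme rise that nobody flags is not.

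**4. Effect on the estimate.** SAP 2.1.2 counts a patient in the DMR denominator who either had the event or was followed through the time point without it. On that rule, a followed patient whose MI went unnoticed, and who had no other event, is counted as event-free and not as missing.

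**5. Size.** The documents give neither the number of further procedures nor a periprocedural MI rate. Let N = 2,000 (protocol 2.3), p = share of patients with a further Absorb GT1 procedure, q = share of those with an enzyme-only MI, and r = share of such MIs that sites report anyway. Then

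missed = N × p × q × (1 − r).

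As pure assumptions, take p from 10% to 20% and q from 1% to 5%, with r = 0:

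- low: 2,000 × 0.10 × 0.01 = 2, and 2/2,000 = 0.1 percentage points
- high: 2,000 × 0.20 × 0.05 = 20, and 20/2,000 = 1.0 percentage points

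Setting r = 0 means that sites report none of these events, and each patient is taken to have no other qualifying event. The range is therefore an illustrative upper range for the chosen p and q. Any reporting by sites shrinks it in proportion.

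**The case against.** A reader might infer that any periprocedural MI caused by a second implant goes unrecorded, or that a CK-MB value measured at that procedure has no place in the data set. The documents do not support either statement. The adverse-event rule stands directly beside the form rule in 2.2, and 5.11, 7.1 and 7.5 give a recognised or suspected MI a reporting and adjudication route. Sections 5.3 and 5.4 stand alone, enzymes have their own form, and neither section is expressly restricted to the study procedure.

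It can also be argued that *only* means no new registration: 2.2 concerns registration and says that a follow-up case is not a new one. In addition, section 5 of the public text shows headings without field lists, and a redacted part precedes Attachment 2, so the full content of the form cannot be seen. CK-MB is measured by site standard even at the first procedure. The periprocedural row of the MI table already applies to any PCI, so the rule itself needs no extension.

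Most of this stands, and it narrows the point to silent infarctions that the site does not itself recognise and report. It does not remove the point. If the milder meaning of *only* is intended, the protocol does not say so, and a site that follows the words would leave the enzyme page blank. Measurement by site standard explains missing values, but not why existing values would be entered for one implant and not for the next.

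The objection on size also stands. Both assumed rates come from outside the documents. DMR includes all revascularization, so a patient whose further PCI treats a new lesion during follow-up may already have a DMR event.

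**Conclusion.** The concern holds as a limited gap in ascertainment. On a literal reading of 2.2 and 5.12, a symptom-free periprocedural MI after a further Absorb GT1 procedure is found only through the site's own recognition and adverse-event report, whereas for the first procedure the protocol lists enzyme data for collection. MI, TV-MI, TLF, MACE, TVF and cardiac death/MI may be understated for later implants.

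The size cannot be derived from the documents, and the 0.1 to 1.0 percentage points in the working should not be cited as an estimate. For new lesions treated during follow-up, the form rule applies only before commercial sale, which limits exposure further. The endpoints concerned are all among the other endpoints. The 3-month and 2-year scaffold thrombosis criteria are not directly affected, because thrombosis has its own reporting and image-review route.

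The conclusion rests on reading *only* literally and on 5.12 being a complete list of what the form asks for.

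**What to change.** - In 2.2 (both places) and 5.12, state that the existing 5.3 and 5.4 pages are also entered, where the site has the values, for each additional Absorb GT1 procedure that requires the additional treatment form. This keeps the present limit to the period before commercial sale for follow-up lesions.
- Reword the Attachment 2 footnote so that the baseline biomarker is the value before the procedure in question.

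The cost is some extra data entry, on pages that already exist, for patients with a further Absorb GT1 procedure. The reported MI rate may rise slightly because detection would be more complete. No test is added.

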2.3 Planned Sample Size

Target sample size of the Surveillance is approximately 2,000 patients. Commercial sale of Absorb GT1 beyond the purpose of the Surveillance will be started if the scaffold thrombosis (ST) rate in the 2,000 patients at 3 month is 0.9% or lower (ST rates for patients with Absorb GT1).

2.4 Method

The surveillance consists of two phases as detailed below. All- patients will be continuously registered in each phases. This means that Absorb GT1 must not be used outside of the Surveillance, except in the case of revascularization to the registered patients.

Phase 1 (All- patients):

- 250 patients (approximately 45 sites)
 - Surveillance Sites:

AVJ-301 investigational sites or medical institutions which have a physician with experience of implantation of Absorb GT1 (or previous types of the device) in or outside of Japan (considering possible move of AVJ-301 investigators to another site)

- Main Purpose: To confirm the efficacy of physician training and to establish optimal training for increasing medical institutions participating in post-marketing evaluation. Procedural results will be evaluated sequentially for early feedback to the sites. Therefore, there will be no quantitative goal established to move to Phase 2. However, recommended procedure may be updated as required in order to achieve optimal acute result.
- Lesions to be treated: Per product IFU
- All cases will be treated by imaging-guided implantation technique using IVUS/OCT
 - At least first 150 cases will be analyzed by the core lab.
- Primary Endpoint 1: Exclusion of very small vessels
 - In the ABSORB III trial, very small vessel with RVD < 2.25 mm per core lab QCA was a risk factor of scaffold thrombosis.
 - In the AVJ-301 and the ABSORB III trials, lesions with RVD < 2.25 mm consisted of 14.4% (59/411) and less than 20% of all the lesions registered respectively. Therefore, goal of the training is to exclude these very small vessels.
 - Angiograms and IVUS/OCT images taken during procedure will be sent immediately to the core lab, which will analyze the images and give feedback to the site. Additional training or revision of registration criteria may occur as required in order to exclude almost all lesions with RVD < 2.5 mm from registration by the last half of Phase 1.
- Primary Endpoint 2: Scaffold apposition and complete expansion evaluated by IVUS/OCT (analyzed by the core lab)
 - Descriptive analysis only

Numerical goal will not be set because there is currently no imaging-guided BVS implantation technique established.

However, implantation guidelines will be established upon agreement by Sponsor's medical adviser and the core lab based on results of the clinical studies with this device and imaging-guided metallic stent implantation technique.

IVUS/OCT images taken during procedure will be sent immediately to the core lab, which will analyze the images and give feedback to the site as required. Images of ST, if occurred, will also be sent to the core lab.
 - All core labs will be those located in Japan in order to fulfill the goals mentioned above.

[figure not shown]
Phase 2 (All- patients):

- Until 2000 patients are registered (up to 200 sites)
 - Surveillance sites:
 - Phase 1 sites
 - Sites which have a physician accredited by CVIT, and experience of \geq 100 PCI cases per year.

- Main Purpose: To confirm safety
- Lesions to be treated: Per product IFU unless otherwise instructed
- To be treated by site standard procedure (imaging-guided implantation technique using IVUS/OCT recommended per product IFU)
- Primary Endpoint: ST through 3 months
 - Criteria: ST rate (in 2,000 patients: sum of Phase 1 and Phase 2)
 - ≤ 18 patients (0.9%): To start commercial sale
 - ≥ 19 patients: To investigate the cause and take appropriate actions
- All images of ST, if occurred, will be sent to the core lab.
- At Phase 2, IVUS/OCT images post procedure may be analyzed in the core lab as well. Surveillance sites will cooperate to the Sponsor, if requested.

